#### Human Subject Protections

#### **Subject Selection**

Exclusion criteria include children who have concurrent illnesses requiring glucocorticoid treatment (such as severe asthma), or requiring drugs that markedly alter hydrocortisone metabolism (such as anticonvulsants), and children who cannot be brought into reasonable control with conventional treatment (an unusual occurrence).

The incidence of classical CAH appears to be nearly the same in all ethnic groups, and lower in African Americans (ref: Therrell BL, Jr., Berenbaum SA, Manter-Kapanke V, et al. Results of screening 1.9 million Texas newborns for 21-hydroxylase-deficient congenital adrenal hyperplasia. *Pediatrics* 1998; **101**(4 Pt 1): 583-90. Based upon our previous studies, the anticipated gender and ethnic distribution of this study will reflect the gender and ethnic distribution of the United States population.

The study includes a vulnerable population (children) because treatments designed to address the growth abnormalities in CAH can only be evaluated in subjects who are growing. However, the procedures involved in this study are essentially the same as would be required in children receiving conventional treatment for CAH outside of a study. Additionally, the expertise provided by the study team, may reduce the psychological stress of evaluation compared to some other settings. Moreover, the expertise of the physician team may mitigate some of the physical consequences of the disorder (such as iatrogenic Cushing syndrome), even for those subjects who are in the conventional treatment arm.

#### **Evaluation of Benefits and Risks/Discomforts**

Data from this study will be evaluated annually by the NICHD Data Safety Monitoring Committee.

The potential benefits include a 50% chance of receiving state-of-the-art monitoring and drug adjustment, if one is randomized to conventional treatment, and a 50% chance of receiving the hypothesized benefits of the new investigational regimen, if one is randomized to that arm and if the hypothesized benefits are in fact realized. The psychological assessment has the benefit of identifying an unknown learning disability.

The risks and discomforts of participation in this study include:

(1) pain associated with having an intravenous needle inserted into a hand or arm vein, and the possibility of a bruise;

- (2) the inconvenience of urine collections;
- (3) blood withdrawal: 120 mL per 6 months for the conventional arm. If the leuprolide

stimulation test and ACTH test are omitted, blood withdrawal is 84 mL. For those receiving flutamide, additional blood withdrawal will be necessary for liver function tests: 12 mL in the first 6 months, 6 mL for the subsequent 6 months and 2 mL thereafter. These amounts are within the National Institutes of Health guidelines of 7 mL per kg body weight per 6 weeks. If a child meets this blood limit, certain tests will be omitted.

(4) inconvenience and discomfort of being upright for 2 hours for an upright renin test.

(5) Aromatase inhibitor. Over twenty years of testolactone use, and our own experience with protocols 82-CH-165 and 85-CH-16, have revealed only minor dose-related gastrointestinal side effects and no serious toxicity. This side effect has been observed, but less commonly, with letrozole.

Other than testolactone, letrozole is the aromatase inhibitor with the most reported pediatric experience and with the most clinical experience by investigators at the Clinical Center. No harmful side-effects have been reported.

(6) Flutamide. Aside from infrequent nausea, diarrhea, and dizziness, the most common sideeffect when flutamide was used in prostate cancer has been gynecomastia and breast tenderness (34% of patients). We have found, however, that combined treatment with aromatase inhibitor prevents development of gynecomastia, as was the case during combined spironolactone plus testolactone treatment [8]. Infrequent adverse events reported in the literature include thromboembolic complications [15] and neutropenia [42]. Should the latter develop, the drug will be discontinued immediately.

The most serious adverse effect of flutamide is hepatotoxicity. This risk was not detected in animal or pre-marketing clinical studies. It became apparent through the spontaneous reporting of 15 deaths believed to be due to flutamide-related hepatotoxicity from among the nearly 700,000 flutamide prescriptions for prostate cancer between 1989 and 1991 [43]. The median duration of flutamide treatment among the fatal cases was 2 months, with the longest duration being 7 months. In each fatal case flutamide administration was continued despite evidence of deteriorating liver function. In other cases in which flutamide was discontinued after liver toxicity was recognized, the abnormality of liver function was reversible.

In a study of 1,091 consecutive patients with prostate cancer treated with flutamide, 4 (or 1 in 273) developed significant liver dysfunction during the first month of treatment, which resolved completely with discontinuation of the drug. Thus, liver toxicity due to flutamide usually develops early in the course of treatment. This is the rationale for the schedule of hepatic monitoring in the flutamide-treated patients in this study: every 2 weeks for the initial 3 months of treatment, every month for the next 9 months, and every 3 months thereafter. In addition to the monitoring, each parent will be instructed in the signs and symptoms of liver toxicity and what to do if they should occur (see consent).

If an elevation in liver function tests occurs, the following monitoring will be done. If the liver enzyme values are greater than 3 times the upper limit of normal, flutamide will be discontinued immediately. If the liver enzyme values are elevated but less than a 3-fold increase, liver function tests will be repeated immediately but the drug will not be discontinued. If the elevation is confirmed by repeat testing, the child will have weekly liver function tests for 3 weeks. If the

values are increasing by more than 10%, flutamide will be discontinued. If values are remaining the same (or within 10%), flutamide will be continued and the previous regimen of liver function test monitoring will be resumed with a minimum of monthly evaluations for the first three months. The above monitoring program was developed after consulting both the Food and Drug Administration and an internationally recognized expert on drug-induced hepatic injury. With these precautions, it is believed that the risk of serious hepatic injury, such as occurred in adults before this risk of the drug was recognized [43], can be eliminated. During the 8 years that we have used flutamide, involving approximately 30 children, no hepatotoxicity has been observed.

The use of flutamide during pregnancy may result in ambiguous genitalia in a male fetus. Other potential teratogenic effects are unknown. Ovulation and pregnancy either prior to menarche or in the first 6 months following menarche in girls with classic CAH is extremely unlikely. All female subjects have undergone genital surgery for correction of ambiguous genitalia and many require a second surgery in adolescence before sexual intercourse will be possible. These structural abnormalities further reduce the unlikely possibility of pregnancy. Patients and their parents will be counseled together and separately as to the importance of not becoming pregnant while on flutamide. We will perform a pregnancy test each visit for pubertal girls on flutamide.

(6) Since hydrocortisone dosage will be reduced below that usually employed, some patients may develop symptoms or signs of adrenal insufficiency. We consider that this is unlikely to be a serious risk because; (1) patients will continue to receive an optimal fludrocortisone dose, (2) CAH patients remain capable of producing some endogenous hydrocortisone, and (3) the restricted dosage of approximately 8 mg/m^2/day is equivalent to the most recent estimates of normal production rate and, in concert with the first 2 factors, should prevent any subjects from experiencing adrenal crisis. If, however, symptoms or signs of adrenal insufficiency do occur at this dosage, the hydrocortisone dose will be increased on an individual basis to a dose that does not cause such signs or symptoms.

(7) Efficacy of the new treatment approach. Since the new approach to be tested in this study has only been employed previously in short-term studies, there is the theoretical possibility that its long-term effectiveness could be less than that of conventional therapy. In this event participants randomized to the investigational regimen would miss the full benefit of conventional treatment.

(8) Leuprolide stimulation test. This is a standard test of pubertal onset. It has no known risk.(9) ACTH test. This is a standard test of adrenal function. It has no known risk.

(10) Bone density of the forearm, femur, and lumbar spine will be determined annually by DEXA. (Bone age x-rays of the wrist will also be performed every six months). The maximal tissue dose is 90 mrem to skin of lower back. The total effective dose is less than 1 mrem. Effective dose is the uniform whole-body dose, which is used to relate the dose received by each organ to a single value. The effective dose is well within the RSC guidelines for children of 500 mrem.

(11) Magnetic Resonance Imaging (MRI). This procedure is without known risk and involves no radiation exposure. Approximately 1% of subjects are too claustrophobic to be studied. During the MRI scan, the patient hears rhythmic tapping sounds due to switching on and off of the gradient coils. Subjects are warned of this prior to scanning and most do not find it objectional. Ear plugs are provided. Metal objects are exclusionary criteria and patients will be carefully screened for these exclusionary criteria. There are no known adverse effects of magnetic resonance imaging

but guidelines for use have been established by the FDA. For purposes of this protocol the NIH s MRI units operate well within those guidelines and their use has been previously approved in an IRB protocol for child age volunteers (CC#87-CC-91).

(12) There are possible discomforts associated with talking about topics such as behavior problems, or mental health problems.

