Choice of medication will be based on patient and family preferences. Families will be counseled on the advantages and disadvantages of these two therapies. Both medications are known to effectively suppress the hypothalamic-pituitary-gonadal axis. Known side effects include rash, and local injection site reactions (milder with Deslorelin). Lupron has the advantage of monthly administration and the disadvantage of an increase risk of local injection site abscess formation (Deslorelin may cause redness at the injection site but has not been reported to result in abscess formation). Lupron also may require more dose adjustments in the beginning of therapy. Anaphylactoid reactions are an extremely rare risk for both medications. Children will return to the NIH day hospital 3 months after starting LHRH analog therapy for evaluation of hypothalamic-pituitary-gonadal suppression. Those patients who are currently being treated with Deslorelin (previously under protocol 79-CH-112) will be continued on Deslorelin or switched to Lupron, depending on patient preference.

Once degree of CAH control has been judged optimal, children will be randomized to receive either the regimen of flutamide, testolactone or letrozole, and reduced hydrocortisone dose or conventional treatment (with hydrocortisone and fludrocortisone) until the age of 13 in the girls and 14 in the boys. At that time the regimen of flutamide, testolactone, and reduced hydrocortisone dose will be discontinued in boys so that the subjects can progress through puberty. At age 13 years, girls who are receiving flutamide and testolactone or letrozole therapy will discontinue the aromatase inhibitor therapy (to allow normal progression of puberty) and continue flutamide (to continue androgen blockade). Flutamide therapy will continue until 2 years after menarche or when final height is reached, whichever occurs first.

Children who are also receiving concurrent LHRH analog to suppress central puberty will also discontinue this agent at age 13 in the girls or age 14 in the boys. The operational definition of age 13 or 14 will be the NIH study visit that is closest to their thirteenth or fourteenth birthday. The operational definition of attainment of final height, as in our other long-term trials, will be the study visit at which the incremental growth over the previous 12 months declines to less than 1.5 cm (0.6 inch).

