During flutamide and aromatase inhibitor treatment hydrocortisone dose will be decreased in 4 equal weekly steps to approximately 8 mg/m^2/day. During this month close contact will be maintained with the family by telephone and/or outpatient visits (for local patients), or referring physician visits (for distant patients), to check for symptoms or signs of adrenal insufficiency. If the hydrocortisone dosage of approximately 8 m^2/day produces symptoms or signs of adrenal insufficiency in any subject, the dosage will be adjusted on an individual basis to a dosage that will not cause symptoms or signs of adrenal insufficiency.

Patients will initially be placed on Testolactone 20 mg/kg/day of testolactone. The dose will then be increased at weekly intervals to 30 and then 40 mg/kg/day, which will be the maximum dose for the study (approximately equivalent to the usual maximal adult dose of 2 grams per day).

Patients placed on letrozole will receive a dose comparable to the dose used to suppress estrogens in adult women (1.5 mg per square meter of body surface area). This is the same dose of letrozole used for the treatment of girls with McCune Albright Syndrome.

Flutamide will also be administered in increasing doses. Patients will initially be placed on 5 mg/kg/day of flutamide. The dose will then be increased at weekly intervals to 7.5 and then 10 mg/kg/day, which will be the maximum dose for the study. This is approximately the same dose used to treat men with prostate cancer (750 mg/day, or about 10 mg/kg/day).

Subjects will be evaluated as outpatients, day-hospital patients, or inpatients on the pediatric endocrine ward at 6-month intervals until final adult height is attained. The following evaluations will be made:

- (1) Ten standing height measurements by stadiometer.
- (2) Ten sitting height measurements.
- (3) Weight.
- (4) Bone age.
- (5) Two 24-hour urine collections for cortisol.

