(6) A leuprolide stimulation test, to assess pubertal status of the hypothalamic-pituitarygonadal axis will be performed at the first visit and all subsequent visits after the child has reached a bone age of 10 in boys or 9 in girls, or if there is clinical suspicion of hypothalamic-pituitarygonadal activation (i.e. testicular enlargement in boys, breast tissue in girls). Children who are started on an LHRH analog for central precocious puberty and those who switch LHRH analog medication type will have leuprolide stimulation test performed 3 months after beginning treatment to confirm efficacy of this treatment. Additional leuprolide stimulation testing while receiving an LHRH analog will only be done if clinically indicated. This testing will resume once the patient is taken off LHRH analog therapy. Measurement of gonadotropins by third-generation immunochemiluminometric assays (ICMA) will be done. Blood withdrawal: 12 mL.

(7) Measurement of plasma 17-hydroxyprogesterone, DHEA-S, androstenedione, estradiol, testosterone, cortisol, and ACTH, estradiol starting as near 0800 h as feasible. The morning hydrocortisone dose will be held until after these samples have been obtained. Blood withdrawal: 18 mL.

(8) Blood to be frozen for possible future hormone measurements: 17 mL.

(9) Upright and supine plasma renin activity. Blood withdrawal: 14 mL.

(10) Routine CBC, thyroid panel and SMAC. Blood withdrawal: 8 mL.

(11) One-hour cortrosyn (ACTH) test to assess levels of steroid intermediates in response to ACTH stimulation. Cortisol, 17-hydroxyprogesterone, androstenedione, and DHEA will be measured at time 0 and 60 minutes after ACTH bolus infusion. Blood withdrawal: 24 mL. This test will be performed at the beginning and end of the study, and, if indicated, at some other visits.

(12) Fasting glucose, insulin and leptin levels. Blood withdrawal: 5 mL.

(13) Lipid profile. Blood withdrawal: 2.5 mL.

(14) Plasma and urinary catecholamines and metanephrines Blood withdrawal: 20 mL.

(15) Bone densitometry (DEXA): to be performed at start of treatment, annually thereafter (e.g., every other NIH visit), and at attainment of final adult height, to measure bone density of the forearm, femoral neck, and spine (AP and lateral).

(16) MRI abdomen: to be performed after 2-3 years on the protocol and after the patient's 6th birthday.

(17) Boys will have a testicular ultrasound and girls will have a pelvic ultrasound done

each visit.

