Many children with CAH enrolled in 96CH003 are in special education classes or have documented language or perceptual delays by parental report. Learning disabilities are 6 times more likely to occur in males than females. The role of androgens in this phenomenon is unknown. Sex differences in patterns of brain maturation in children have been found [36]. This sexual dimorphism is of interest in light of the differences in prevalence, age of onset, and symptomatology noted in nearly every neuropsychiatric disorder of childhood onset. Sexually distinct patterns of normal brain development may be due to the X or Y chromosomes, effects of hormones, or environmental factors. Several studies on CAH children have suggested that CAH females are similar to males in both their behavior and/or cognition. For example, a study of CAH control females with equivalent general intelligence found CAH patients to have inferior verbal vs. visual and arithmetic scores typical of male vs. female differences [37]. CAH females have been shown to have improved spatial skills, typical of males [38]. Studies of gender-related behavior have shown that CAH females have more masculine type orientation than their unaffected sisters [39] and have more masculinized play preferences [40]. These type of data have been interpreted as a consequence of early in utero androgen exposure since testosterone is known to promote development of the right hemisphere and delays maturation of the left hemisphere. We hypothesize that in CAH females, the organization of the brain is more like males than females, while CAH boys are more like unaffected males.

(22) At the time of menarche, girls will be asked to keep a calendar documenting their menstrual history.

Due to the known hepatotoxicity of flutamide in some patients (see Risks below), patients who randomize to the flutamide and aromatase inhibitor arm will have liver function tests drawn by their local physician every 2 weeks for the first 3 months, then once a month for the next 9 months, then every 3 months for the duration of the study. Parents will also be carefully instructed about the signs and symptoms of liver toxicity and the procedure to follow if such symptoms occur (see consent). We have not, however, observed flutamide-associated liver toxicity in any child receiving flutamide during our initial 6-month pilot study or the ongoing current study.

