#### Monitoring and Criteria for Withdrawal of Subjects from Study

Patients will be monitored every 3 months, with visits alternating between their local physician and NIH (every 6 month visit to NIH). At the visit to the local physician, a single blood sample

will be obtained and sent to NIH for analysis of the same hormonal measures and blood chemistries that are performed during NIH visits (see protocol section above). The other monitoring during NIH visits has been described in detail above.

In addition to this monitoring, patients who are randomized to flutamide will receive intensive monitoring of liver function as a precaution against flutamide-associated liver toxicity (see Risks below). This monitoring will consist of a blood sample to determine liver function every 2 weeks for the initial 3 months, every month for the next 9 months, and every 3 months thereafter.

Patients who experience flutamide-associated liver toxicity (the estimated incidence is 1 in 273 patients), or who do not tolerate the flutamide and aromatase inhibitor regimen, will be withdrawn from this treatment arm and followed on conventional treatment so that their outcome will be available for an intention-to-treat analysis. We will also ask patients who elect to withdraw from the study to continue to make semiannual height measurements at home and to return to NIH for one final height and weight measurement once they attain the final height criteria.

Since CAH is a chronic disorder requiring lifelong treatment, and since the final height of all subjects is important for the performance of an intention-to-treat analysis, we do not foresee circumstances that would lead us to withdraw a subject from study. If an unrelated illness, such as chronic active hepatitis, were to preclude use of the investigational regimen, we would nonetheless wish to follow the subject on the conventional treatment.

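### Flutamide must stop at once for neutropenia, but the only blood count named is 6-monthly, so a symptomless case could go unseen for up to about 26 weeks; a count at the 3-monthly local draw would halve that

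*Combined protocol and SAP*

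**What the plan says.** All references are to the Combined protocol and SAP.

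- **Stopping rule.** Evaluation of Benefits and Risks/Discomforts, item (6) Flutamide, names thromboembolic complications and neutropenia as infrequent literature reports. Of neutropenia it says: "Should the latter develop, the drug will be discontinued immediately". It gives no neutrophil threshold, repeat step or count schedule.
- **Blood count.** The Protocol section has subjects evaluated as outpatients, day-hospital patients or "inpatients on the pediatric endocrine ward at 6-month intervals until final adult height is attained". Item (10) of that evaluation is "Routine CBC, thyroid panel and SMAC". No other blood count is named.
- **3-monthly local sample.** Monitoring and Criteria for Withdrawal places a local visit midway between NIH visits, with one blood sample sent to NIH for "analysis of the same hormonal measures and blood chemistries that are performed during NIH visits". A CBC is neither named nor ruled out.
- **Flutamide-arm draws.** Children in this arm "will have liver function tests drawn by their local physician every 2 weeks for the first 3 months", then monthly for 9 months, then every 3 months. These draws are described as liver function only.
- **Consequence of stopping.** Children with liver toxicity, or who do not tolerate the regimen, "will be withdrawn from this treatment arm and followed on conventional treatment".
- **Duration.** Randomised treatment runs "until the age of 13 in the girls and 14 in the boys", with flutamide continuing longer in girls.

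**The concern.** An immediate stop can act only as fast as the condition is found. For liver toxicity the plan supplies a dense schedule, a threshold of 3 times the upper limit of normal, repeat testing of smaller rises, and rules for stopping or continuing. For neutropenia it supplies the stop alone.

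Two things are at stake. A child with symptomless neutropenia could stay on a drug that the plan says must be stopped at once. And because nothing defines or confirms a low count, a single transient value, if read as intolerance, could move a child to conventional treatment for good.

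**Working it through.** The plan states no detection lag, so there is no figure to reproduce. The longest scheduled lag is the longest gap between consecutive counts. If onset is equally likely at any time, the mean lag is half of a constant gap.

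**Inputs from the documents:** CBC every 6 months (Protocol section); local sample every 3 months (Monitoring section); 30 children per group (Analysis of Study). One month is 365.25/12 days.

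**Lag**
- Counts at NIH visits only: gap = 365.25/2/7 = 26.1 weeks; mean 13.0.
- Counts also at the local sample: gap = 365.25/4/7 = 13.0 weeks; mean 6.5.

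The second line is both the present position, if the local sample already includes a CBC, and the position after the fix. These are scheduled lags. Actual ones could be longer, since tests may be omitted at the blood limit and missed draws are not reported as deviations.

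**Added counts and blood.** 4 − 2 = 2 per child-year, or 30 × 2 = 60 per year with all 30 children on flutamide. At 1 mL each (assumed) that is 2 mL per child-year.

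**Incidental low counts.** Expected children flagged per year = 30 × (1 − (1 − p)^n), where p is the chance that one count is incidentally low (assumed, counts independent) and n is counts per year.

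| p | n = 2 | n = 4 | added |
|---|---|---|---|
| 0.1% | 0.06 | 0.12 | 0.06 |
| 0.5% | 0.30 | 0.60 | 0.30 |
| 2% | 1.19 | 2.33 | 1.14 |

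**True cases.** The documents give no neutropenia rate. If it equalled the liver-toxicity figure ("the estimated incidence is 1 in 273 patients"), 30/273 = 0.11 cases would be expected, with a chance of at least one of 1 − (272/273)^30 = 10.4%. Over an assumed 1 in 1,000 to 1 in 50, the expectation is 30/1000 = 0.03 to 30/50 = 0.6.

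**Comparison: a CBC at every liver draw.** Take draws at weeks 2, 4, …, 12, then monthly to week 52: 6 + 9 = 15 in year 1.
- Gaps: 2 weeks in months 1–3; about 4.3 weeks in months 4–12, with one of 5.33 at the changeover; 13 weeks after year 1.
- Year-1 mean lag: (6 × 2² + 5.33² + 8 × 4.33²)/(2 × 52) = 1.95 weeks.
- Children flagged in year 1 at p = 0.5%: 30 × (1 − 0.995^15) = 2.2, against 0.3 with NIH counts only.
- Added blood in year 1: 15 − 2 = 13 counts, or 13 mL, on a liver-test allowance of 12 + 6 = 18 mL, a rise of 72%.

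**The case against.** The strongest reply is that the plan contains no error. The stopping rule describes a response, a CBC is scheduled at every NIH visit, and nothing in the documents shows that 6 months is too long for an event called infrequent. A reader might infer that the plan contradicts itself or leaves neutropenia unmonitored. The text does not support that: the 6-monthly CBC serves the rule, and a count prompted by symptoms could trigger the stop sooner. Family instructions on symptoms may be in the consent pages, which were not available. The point is therefore confined to symptomless cases between scheduled counts.

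The 26-week figure also depends on a reading. The local sample is said to cover the same measures as NIH visits, and the CBC shares an item with the SMAC panel, so some may take it as included. The wording names only hormones and chemistries, which makes 26 weeks the more natural reading, but 13 cannot be excluded.

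A reader might go further and infer that the count should follow the full liver schedule because flutamide toxicity comes early. That timing is documented for liver toxicity alone; nothing is said about when neutropenia begins. On the assumed rates, that schedule flags about 2.2 children in year 1 against 0.11 true cases. Blood is a further constraint. For an assumed 12 kg child the limit is 7 × 12 = 84 mL per 6 weeks, and one NIH visit takes 84 mL without the leuprolide and ACTH tests or 120 mL with them. Extra draws close to a visit could displace other tests. This objection stands against the full schedule. It bears much less on the local draw, which on schedule falls about 13 weeks from either neighbouring NIH visit.

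**Conclusion.** The gap is real but small. On the natural reading, the longest scheduled time to detect symptomless neutropenia is about 26 weeks (mean 13 if onset is uniform). A CBC at the existing 3-monthly local draw brings it to about 13 weeks (mean 6.5). If that sample already includes a CBC, the lag does not change; the wording is only clarified, and the missing threshold and repeat rule remain.

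Priority is low. The event is called infrequent, no rate or onset time is given, and the expected 0.11 cases borrows a rate from a different toxicity. The incidental-flag figures rest on assumed values of p. The documents do not say how many children are still on flutamide, and the benefit scales with that number.

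A reader might also infer bias between arms or harm to the height comparison. The documents give no basis for either: children who stop are still followed for the intention-to-treat analysis, and the expected numbers are very small. No effect on the primary endpoint is claimed.

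**What to change.** 1. In Monitoring and Criteria for Withdrawal, add a CBC with differential to the 3-monthly local draw for children on flutamide.
2. In item (6) Flutamide, state a neutrophil threshold. Say that flutamide is held at once on a count below it, that the count is repeated within about 1 week, and that flutamide may resume if the repeat is normal. The stop stays immediate; what changes is that an unconfirmed low count does not end treatment permanently.
3. Update the blood volumes in the risk section by about 1 mL per 6 months.

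Counts at the 2-weekly and monthly liver draws in year 1 can be left as an option for the investigators.

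The cost is a short amendment and about 2 extra counts per child-year, with no extra scheduled visit or needle. At the assumed 0.5%, about 0.3 more children per year in an arm of 30 would be flagged, each needing one repeat draw and about a week off flutamide. That is roughly 0.3 of 30 × 52 = 1,560 child-weeks. If the local sample already includes a CBC, item 1 costs only the wording.
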